#### **10.3.4 Assessment of Causality**

- The investigator is obligated to assess the relationship between study intervention, imaging device(s), study procedures and each occurrence of each AE/SAE/ADE.
- A “reasonable possibility” of a relationship conveys that there are facts, evidence, and/or arguments to suggest a causal relationship, rather than a relationship cannot be ruled out.
- The investigator will use clinical judgment to determine the relationship.
- Alternative causes, such as underlying disease(s), concomitant therapy, and other risk factors, as well as the temporal relationship of the event to study intervention administration will be considered and investigated.
- The investigator will also consult the IB and/or product information, for marketed products, in the assessment.
- For each AE/SAE/ADE, the investigator must document in the medical notes that they have reviewed the AE/SAE/ADE and has provided an assessment of causality.
- There may be situations in which an SAE/ADE has occurred and the investigator has minimal information to include in the initial report to the sponsor. However, it is very important that the investigator always make an assessment of causality for every event before the initial transmission of the SAE/ADE data to the sponsor.
- The investigator may change their opinion of causality in light of follow-up information and send a SAE/ADE follow-up report with the updated causality assessment.
- The causality assessment between study intervention is 1 of the criteria used when determining regulatory reporting requirements.

Following a review of the relevant data, the causal relationship between the study intervention and each AE/SAE/ADE will be assessed by answering “yes” or “no” to the question “Do you consider that there is a reasonable possibility that the event may have been caused by the study intervention?”

When making an assessment of causality, the following factors are to be considered when deciding if there is evidence and/or arguments to suggest there is a “reasonable possibility” that an AE/SAE/ADE may have been caused by the study intervention (rather than a relationship cannot be ruled out) or if there is evidence to reasonably deny a causal relationship:

- Has the participant been administered study intervention?
- Plausibility (i.e., could the event have been caused by the suspect study intervention? Consider biologic and/or pharmacologic mechanism, half-life, literature evidence, drug class, preclinical and study data, etc.)

- Dechallenge/rechallenge:
  - Dechallenge: Did the AE/SAE/ADE resolve or improve after only stopping the dose of the suspect study intervention without any treatment?
  - Rechallenge: Did the AE/SAE/ADE reoccur if the suspected study intervention was reintroduced after having been stopped?
- Laboratory or other test results: a specific laboratory investigation supports the assessment of the relationship between the AE/SAE/ADE and the study intervention (e.g., based on values pre-, during and post-treatment)
- Available alternative explanations independent of study intervention exposure, such as other concomitant interventions, device malfunctions, medical history, concurrent or underlying disease, risk factors including medical and family history, season, location, etc., and strength of the alternative explanation
- Temporal relationship between exposure to the study intervention and AE/SAE/ADE onset and/or resolution. Did the AE/SAE/ADE occur in a reasonable temporal relationship to the administration of the study intervention?
- Finally, judging which are more likely based on all the above contents, factors of reasonable possibility or confounding factors, comprehensive judgment of plausibility will be provided.

There may be situations in which an SAE/ADE has occurred and the investigator has minimal information to include in the initial report to the sponsor. While it is very important that the investigator always assesses causality for every event before the initial transmission of the SAE data to the sponsor, the initial report should be submitted without delay (i.e., within 24 hours of awareness). With limited or insufficient information about the event to make an informed medical judgment and in absence of any indication or evidence to establish a causal relationship, a causality assessment of “no” is to be considered. In such instance, the investigator is expected to obtain additional information regarding the event as soon as possible and to re-evaluate the causality upon receipt of additional information. The medically qualified investigator may revise their assessment of causality in light of new information regarding the SAE/ADE and shall send an SAE/ADE follow-up report and update the eCRF with the new information and updated causality assessment.

### **Device Relatedness**

Events will be classified as device related if they meet the following criteria:

- Not Related: Any reaction that does not follow a reasonable temporal sequence from administration of the device or surgical procedure, or study intervention AND that is likely to have been produced by the subject’s clinical state or other modes of therapy administered to the subject.
- Related: A reaction that follows or may follow a reasonable temporal sequence from administration of the device, surgical procedure, or study intervention AND that follows a known response pattern to the suspected device/surgical procedure/study intervention.

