## **2.3 Risk/Benefit Assessment**

### **2.3.1 Risk Assessment**

In the clinical studies completed to date, ASP5354 has been shown to be safe and well tolerated given as a single intravenous dose up to 24 mg. One of the most frequently reported adverse events (AEs) was green coloration of the urine. ASP5354 is excreted into the urine through the kidneys due to its hydrophilic nature. It is expected that all participants will have green coloration of the urine with ASP5354 administration.

ASP5354 is a new chemical entity administered intravenously. Unlike ICG, it does not contain iodine and no hypersensitivity reactions have been observed for ASP5354 in the clinical studies completed to date. In general, the ICG-related hypersensitivity has been attributed to iodine [Bjerregaard et al, 2013]. Although it remains a potential risk, the use of ASP5354 will be in surgical suites/operating rooms, which are fully equipped to manage a hypersensitivity reaction should it occur.

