### **10.3.3 Adverse Device Effect (ADE)**

#### **10.3.3.1 Definition of ADE**

- Any adverse event related to the use of device (includes all hardware components).
  - Includes any event that is a result of a user error or intentional misuse.

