#### **10.3.3.2 Definition of Unanticipated adverse device effect (UADE)**

- UADE is any serious adverse effect on health or safety, any life-threatening problem or death caused by, or associated with a device, if that effect, problem, or death was not previously identified in nature, severity, or degree of incidence in the application; or any other unanticipated serious problem associated with a device that relates to the rights, safety, or welfare of participants. Note the reporting of UADEs should follow reporting requirements for SAEs/serious adverse device effects.

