5.5.1 Adverse Events

AEs will be assessed by evaluation of the following variables:

- Treatment-emergent adverse events (TEAEs; frequency, severity, seriousness and relationship to study drug)
 - TEAE is defined as an AE observed after ASP5354 administration and up to the follow-up period.
 - If the AE occurs on Day 1 and the onset check box is marked “Onset after study drug taken” or both onset check boxes “Onset before study drug taken” and “Onset after study drug taken” are marked or left blank, then the AE will be considered treatment emergent.
 - If the AE occurs on Day 1 and the onset check box is marked “Onset before study drug taken”, then the AE will not be considered treatment emergent.
 - If a participant experiences an event both during the screening period and during the treatment period, the event will be considered as TEAE only if it is reported with the new start date (i.e., as a new AE).
 - Any AEs with onset dates completely missing will be considered TEAEs in summaries unless the investigator has noted on the CRF the event began prior to treatment. AEs with partially missing onset dates will be assumed TEAEs unless the available portion of the date indicates that the onset was strictly before start of study medication.
 - A drug-related TEAE is defined as any TEAE with possible relationship to study treatment as assessed by the investigator or with missing assessment of the causal relationship.
- Serious adverse events (SAEs) include adverse events that are flagged as serious by the investigator on the eCRF, or upgraded by the Sponsor based on review of the European Medicines Agency’s list of Important Medical Events.
- The frequency and percentage of participants with iatrogenic ureteral injury (IUI) or hypersensitivity which will be considered adverse events of special interest (AESIs).

- The frequency and percentage of participants with green coloration of urine.
- Adverse device effects (ADEs) include adverse events that are flagged as related to the device by the investigator on the eCRF.

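### The device-relatedness rule mixes device, surgery and drug and leaves some events in no class, so ADE counts are at risk of misclassification

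*Protocol*

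**What the plan says.** The Device Relatedness text at the end of protocol Section 10.3.4 presents itself as a classification rule: "Events will be classified as device related if they meet the following criteria". It has two classes.

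- Related has a timing part, "Related: A reaction that follows or may follow a reasonable temporal sequence from administration of the device, surgical procedure, or study intervention", and a second part that must also hold: "AND that follows a known response pattern to the suspected device/surgical procedure/study intervention".
- Not Related begins "Any reaction that does not follow a reasonable temporal sequence from administration of the device or surgical procedure, or study intervention AND" and adds that the event is likely to come from the participant's clinical state or other therapy.

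Three other places bear on it.

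- Section 10.3.3.1 defines an ADE by the device alone: "Any adverse event related to the use of device (includes all hardware components".
- Section 10.3.3.2 defines an unanticipated adverse device effect (UADE) as a serious effect, linked to a device, that "was not previously identified in nature, severity, or degree of incidence in the application".
- The opening of Section 10.3.4 obliges the investigator to assess drug, imaging device and study procedures for each event, naming each one.

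SAP Section 5.5.1 sets the source of the count: "Adverse device effects (ADEs) include adverse events that are flagged as related to the device by the investigator on the eCRF". SAP Section 6.5.1 puts ADEs in the adverse event overview and tabulates them by system organ class and preferred term, apart from the TEAE tables.

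**The concern.** A rule headed as device relatedness should separate device effects from the rest. This one lets surgery and drug satisfy both parts of Related, and in this trial all three exposures fall in the same operating session. Section 6.1.1 times dosing at roughly 30 minutes before the ureter is expected to be seen, so the timing part separates nothing.

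The known-pattern requirement works in the other direction. It shuts out the kind of device event that has not been seen before, which is part of what the UADE definition exists to capture.

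At stake is the ADE table, the SAP's only dedicated summary of device safety. It could fill with drug and surgical events and miss new device effects. ADEs also go to the sponsor on a worksheet within 24 hours (Section 7.3.1.1), so literal use would generate needless expedited paperwork for an expected drug effect.

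**Working it through.** The plan states no figure to reproduce here. The check is one of logic, followed by one count.

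**Step 1. Write the rule as conditions.** Let T = plausible timing after device, surgery or drug; K = known pattern of response to any of the three; C = likely due to clinical state or other therapy. Then Related = T and K, and Not Related = (not T) and C.

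| T | K | C | Class |
|---|---|---|---|
| 1 | 1 | 0 | Related |
| 1 | 1 | 1 | Related |
| 0 | 0 | 1 | Not Related |
| 0 | 1 | 1 | Not Related |
| 1 | 0 | 0 | neither |
| 1 | 0 | 1 | neither |
| 0 | 0 | 0 | neither |
| 0 | 1 | 0 | neither |

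Of the 8 combinations, 2 are Related, 2 are Not Related and 4 have no class. These are combinations, not event frequencies. The two rows with T = 1 and K = 0 matter most, because a new device signal would appear there.

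**Step 2. Vary the true cause, with T = 1.**

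| True cause | Pattern known | Rule as written | Device-only, no known-pattern test |
|---|---|---|---|
| Device | yes | Related | Related |
| Device | no | neither | Related |
| Surgery | yes | Related | Not Related |
| Surgery | no | neither | Not Related |
| Drug | yes | Related | Not Related |
| Drug | no | neither | Not Related |

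The written rule does not depend on the cause at all; it depends only on whether the pattern is known.

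**Step 3. Compare with the UADE definition.** That definition is met by novelty in nature, in severity or in degree of incidence. An effect new in nature has K = 0 and cannot be Related. An effect new only in severity or incidence can still have K = 1 and be Related. The conflict is therefore confined to novelty in nature.

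**Step 4. Put a size on one term.** Section 2.3.1 says of the drug: "It is expected that all participants will have green coloration of the urine with ASP5354 administration". Section 7.2.6.1 has abnormal urine colour recorded as an AE when observed. Planned enrolment is 84 + 10 + 13 = 107, or 84 + 13 = 97 if nobody enters the moderate/severe cohort. If every site applies the rule literally and every case is recorded, green urine gives up to 107/107 = 100% ADEs. If every site follows Section 10.3.3.1, it gives 0/107 = 0%.

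**Step 5. What happens to an unclassed event.** The SAP counts an event with missing drug causality as drug related. It gives no matching rule for a missing device flag, so an event left blank on that item would not enter the ADE table.

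**The case against.** The strongest reply is that no site would use the rule this way. The heading says device, Section 10.3.3.1 is clear, and Section 10.3.4 asks for drug, device and procedures to be assessed by name. The second part of Related speaks of the suspected cause, which can be read as whichever of the three is under suspicion. The SAP relies on the investigator's flag and does not cite the Device Relatedness text. Nor need expected green urine be recorded as an AE in everyone: the renal-impairment study at 3 mg, as described in Section 4.2, reports 7 TEAEs in 28 participants and none is urine colour.

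Much of this stands, and it makes 107 an upper bound. It does not rescue the rule. Even on the charitable reading, the known-pattern requirement and the unclassed events remain, and no other section gives device criteria, since the yes/no causality question is put for the study intervention.

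A reader might go further and infer that UADE detection fails. The documents do not support that. Section 10.3.3.2 needs only a causal or associative link to a device, not the Related class. UADEs follow SAE reporting, all SAEs go to the sponsor within 24 hours whatever their cause (Section 7.3.1), the sponsor evaluates them (Section 10.3.7), and device complaints are reported even without harm (Section 7.3.1.1).

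These backstops are partial. The minimum report content in Section 10.3.7 lists causality to the study intervention but not to the device, so a serious event can arrive without device attribution. A non-serious new device effect has no SAE route, unless it is one of the two events of special interest, which use the SAE worksheet. An unflagged event after dosing does stay in the TEAE tables and listings, so it loses its device label rather than disappearing.

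**Conclusion.** The rule is wrong as stated and must be reconciled with Sections 10.3.3.1 and 10.3.3.2 and with the opening of 10.3.4. Read literally, it classes known drug and surgical reactions as device related, cannot class a device effect new in nature as Related, and leaves events linked in time without a known pattern in no class.

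The consequence is a risk of misclassification in the ADE summaries. For green urine alone the range is 0 to about 107 participants. Where the trial falls in that range cannot be known, because the eCRF wording and completion guideline are not in the documents. A reader might conclude that the ADE counts are wrong, or that no unanticipated device effect can be classed as Related. Neither follows: the counts are sound if sites work from Section 10.3.3.1, and effects new only in severity or incidence can still be Related.

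For UADEs the remaining risk is missing device attribution of effects new in nature. Safety is descriptive, without hypothesis tests, and the primary and key secondary efficacy analyses are untouched.

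**What to change.** In the Device Relatedness text:

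1. Limit both criteria to the imaging device, removing surgery and drug.
2. Replace the known-pattern requirement with the reasonable-possibility standard already in Section 10.3.4, restated for the device. Drug causality stays on its existing yes/no question.
3. Define Not Related as the complement of Related, so that every event has exactly one class.

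Before database lock, run one query round on AEs flagged device related and on AEs with no device classification. If enrolment is already complete (an assumption; the planned period ran to 4Q2024 and the current SAP is dated February 2025), this round is the part that still changes the data.

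The cost is a protocol wording change, an update to the eCRF completion guideline, a site note and a small amount of re-review.

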### 10.3.5 Assessment of Severity

Adverse events, including abnormal clinical laboratory values, will be graded using the NCI CTCAE guidelines, version 5.0. The items that are not stipulated in the NCI CTCAE version 5.0 will be assessed according to the criteria below and entered into the eCRF:

**Table 7 Grading Scale Defining the Severity of an Adverse Event**

Grade	Assessment Standard
1 - Mild	Asymptomatic or mild symptoms, clinical or diagnostic observations only; intervention not indicated
2 - Moderate	Minimal local or noninvasive intervention indicated; limiting age-appropriate instrumental ADL 
3 - Severe	Medically significant but not immediately life-threatening, hospitalization or prolonged hospitalization indicated; disabling; limiting self-care ADL 
4 - Life-threatening	Life-threatening consequences, urgent intervention indicated
5 - Death	Death related to AE

ADL: activities of daily living; AE: adverse event

- 1      Instrumental ADL refers to preparing meals, shopping for groceries or clothes, using the telephone, managing money, etc.
- 2      Self-care ADL refers to bathing, dressing and undressing, feeding self, using the toilet, taking medications and not bedridden.

### 10.3.6 Recording and Follow-up of AEs/SAEs and/or ADEs

#### AE, SAE and ADE Recording

- When an AE/SAE/ADE occurs, it is the responsibility of the investigator to review all documentation (e.g., hospital progress notes, laboratory reports, and diagnostics reports) related to the event.
- The investigator will then record all relevant AE/SAE/ADE information in the eCRF.
- It is not acceptable for the investigator to send photocopies of the participant's medical records to the sponsor in lieu of completion of the eCRF.
- There may be instances when copies of medical records for certain cases are requested by the sponsor. In this case, all participant identifiers, with the exception of the participant number, will be redacted on the copies of the medical records before submission to the sponsor.
- The investigator will attempt to establish a diagnosis of the event based on signs, symptoms, and/or other clinical information. Whenever possible, the diagnosis (not the individual signs/symptoms) will be documented as the AE/SAE/ADE.

#### Follow-up of AEs/SAEs/ADEs

- The investigator is obligated to perform or arrange for the conduct of supplemental measurements and/or evaluations as medically indicated or as requested by the sponsor to elucidate the nature and/or causality of the AE/SAE/ADE as fully as possible. This may include additional laboratory tests or investigations, histopathological examinations, or consultation with other healthcare professionals.

- If a participant dies during participation in the study or during a recognized follow-up period, the investigator will provide the sponsor with a copy of any postmortem findings including histopathology.
- New or updated information will be recorded in the originally completed eCRF.
- The investigator will submit any updated SAE or ADE data to the sponsor within 24 hours of receipt of the information.

#### **10.3.7 Reporting Procedures for SAEs/ADEs/Medical Device Deficiencies**

The investigator must complete and submit an SAE or ADE worksheet containing all information that is required by local and/or regional regulations to the sponsor by fax or email immediately (no later than within 24 hours of obtaining knowledge of the event).

The SAE or ADE worksheet must be signed by a medically qualified investigator (as identified on delegation of authority log). Signature confirms accuracy and completeness of the SAE/ADE data, as well as the investigator causality assessment including the explanation for the causality assessment.

For contact details, see [\[Contact Details of Sponsor's Key Personnel\]](#). Fax or email the SAE/special situations or the ADE worksheet to:

Astellas Pharma Global Development Inc.  
Global Pharmacovigilance  
**North America [contact]  
**North America alternate [contact]  
**International [contact]  
**Email:** [contact]

If there are any questions, or if clarification is needed regarding the SAE/ADE/medical device deficiency, please contact the sponsor's medical monitor/study physician or their designee [\[Contact Details of Sponsor's Key Personnel\]](#).

Follow-up information for the event should be sent promptly (as soon as available, but no longer than within 7 days of the initial notification).

Full details of the SAE/ADE/medical device deficiency should be recorded on the medical records and SAE/special situation or ADE worksheet.

The following minimum information is **required**:

- International study number/study number
- Participant number, sex and age
- Date of report
- Description of the SAE/ADE/medical device deficiency (event and seriousness criteria)
- Causal relationship to the study intervention (including reason)
- Drug provided (if any)

The sponsor or sponsor's designee will medically evaluate the SAE/ADE/medical device deficiency and determine if the report meets the requirements for expedited reporting based on seriousness, causality, and expectedness of the events (e.g., SUSAR reporting) according

to current local/regional regulatory requirements. The sponsor or sponsor's designee will submit expedited safety reports to competent authorities and concerned ethics committee per current local regulations, and will inform the investigator of such regulatory reports as required. Investigators must submit safety reports as required by their IRB/IEC within timelines set by regional regulations (e.g., European Medicines Agency, Food and Drug Administration [FDA]) where required. Documentation of the submission to and receipt by the IRB/IEC of expedited safety reports should be retained by the study site. In the US, FDA expedited IND reporting guidelines will be followed.

The sponsor or sponsor's designee will also evaluate any ADEs/medical device deficiencies and determine if the report meets the requirements for expedited reporting.

The sponsor will notify all investigators responsible for ongoing clinical studies with the study intervention of all SUSARs, which require submission per local requirements (IRB/IEC).

Investigators should provide written documentation of IRB/IEC notification for each report to the sponsor.

The investigator may contact the sponsor's medical monitor/study physician for any other problem related to the rights, safety or well-being of the participant.

